1.0 STUDY OBJECTIVES

1.1 Co-Primary Objectives

- 1.1.1 Phases II and III: To evaluate safety of the investigational agent.
- 1.1.2 Phase II: To determine efficacy of the investigational agent to reduce the duration of COVID-19 symptoms through study day 28.
- 1.1.3 Phase II: To determine the efficacy of the investigational agent to increase the proportion of participants with nasopharyngeal (NP) SARS-CoV-2 RNA below the lower limit of quantification (LLoQ) at study days 3, 7, 14, and 28.
- 1.1.4 Phase III: To determine if the investigational agent will prevent the composite endpoint of either hospitalization or death through study day 28. Hospitalization is defined as ≥ 24 hours of acute care, in a hospital or similar acute care facility, including Emergency Rooms or temporary facilities instituted to address medical needs of those with severe COVID-19 during the COVID-19 pandemic.

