7.1 Definitions of Adverse Events

Adverse Event

An adverse event (AE) is any unfavorable and unintended sign (including an abnormal laboratory finding), symptom, or diagnosis that occurs in a study participant during the conduct of the study REGARDLESS of the attribution (i.e., relationship of event to medical treatment/investigational agent/device or procedure/intervention). This includes any occurrence that is new in onset or aggravated in severity or frequency from the baseline condition.

The scale used in the Study Diary for participant symptoms does NOT equate to the AE grading as found in the Division of AIDS Table for Grading the Severity of Adult and Pediatric Adverse Events (DAIDS AE Grading Table), corrected Version 2.1, July 2017.

Sites should grade participant symptoms as they normally would according to the DAIDS AE Grading Table.

Serious Adverse Events (SAEs)

An SAE is defined as any untoward medical occurrence that results in any of the following outcomes:

- results in death
- is life-threatening
- requires inpatient hospitalization or prolongation of existing hospitalization
- results in persistent or significant disability/incapacity
- is a congenital anomaly/birth defect.
- is an important medical event that may not be immediately life threatening or result in death or hospitalization but may jeopardize the participant or may require intervention to prevent one of the other outcomes listed in the definition above).

Adverse Events of Special Interest

An adverse event of special interest (AESI) (serious or nonserious) is defined as an AE or SAE of scientific and medical concern specific to the investigational agent, for which ongoing monitoring and rapid communication by the investigator to the sponsor could be appropriate.

See appendix/appendices for AESIs related to specific investigational agents.

Suspected Unexpected Adverse Events

A Suspected Unexpected Serious Adverse Reaction (SUSAR) is defined as a serious adverse reaction, the nature or severity of which is not consistent with the applicable product information (e.g., Investigator's Brochure for an unapproved investigational product).

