7.3 Recording Adverse Events

Post entry, the following must be recorded on the eCRFs within 72 hours:

- Grade ≥ 2 AEs
- AEs that led to a change in study treatment/intervention regardless of grade

Post entry, the following must be recorded on the eCRFs within 24 hours:

- AEs meeting SAE definition
- AESIs

Information to be collected includes the following:

- study product group (investigational agent/placebo)
- route of administration
- dose
- event term
- time of onset
- investigator-specified assessment of severity and relationship to the investigational product
- time of resolution of the event
- seriousness
- any required treatment or evaluations
- outcome

Adverse events resulting from concurrent illnesses, reactions to concurrent illnesses, reactions to concurrent medications, or progression of disease states must also be reported. All AEs will be followed to adequate resolution. The MedDRA will be used to code all AEs.

Any medical condition that is present at the time that the participant is screened but does not deteriorate should not be reported as an AE. However, if it deteriorates at any time during the study, it should be recorded as an AE with a descriptive modifier (e.g., "Exacerbation of," "Worsening of," "Deterioration of") the event.

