10.2.2 Phase III: Primary Outcome Measures

10.2.2.1 Efficacy: Death from any cause or hospitalization during the 28-day period from and including the day of the first dose of investigational agent or placebo. Hospitalization is defined as \geq 24 hours of acute care, in a hospital or similar acute care facility, including Emergency

Rooms or temporary facilities instituted to address medical needs of those with severe COVID-19 during the COVID-19 pandemic.

10.2.2.2 Safety: New Grade 3 or higher AE through 28 days.

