Note that the timing of interim analyses based on number of participants who have been hospitalized or have died is based on an expected number of hospitalizations and deaths across the two arms combined of 95. This number is calculated under the assumed design parameters, i.e., assuming a proportion hospitalized/dying of 15% in the placebo control group and a relative reduction of 50% giving a proportion hospitalized/dying for the investigational agent of 7.5%, and a sample size of 421 in each group.

As a stopping guideline for greater efficacy of an investigational agent compared with placebo, the O'Brien and Fleming boundary will be used. The stopping guideline will be implemented using the Lan-DeMets spending function approach to allow for the possibility of changes in the timing of interim analyses and/or additional (or fewer) interim analyses if recommended by the DSMB. Formal details of the expected maximal information and calculation of information time will be provided in the Statistical Analysis Plan. In considering possible modifications to the study or termination of the study for efficacy, the DSMB may consider interim results for the secondary outcome of death. For example, the DSMB might make recommendations based on a high level of evidence for a difference between randomized groups in the proportion dying. In these contexts, a "high level of evidence" might be based on application of the O'Brien and Fleming stopping guideline to the death outcome. In these circumstances, consideration should also be given to the increased risk of a Type I error.

There is the possibility that differences between the treatment groups may be observed early in follow-up. However, the overall goal of the study is to prevent hospitalization and deaths regardless of the timing, and therefore the focus of the treatment group comparisons will be at day 28.

Stopping Enrollment to an Investigational Agent Because of Lack of Effect

If enrollment to the study is fast, there may be limited opportunity to stop enrollment to a specific investigational agent before the target of 421 participants randomized to that agent is complete (because it will take time to achieve follow-up of participants and additional time to analyze and review

results). However, if the rate of enrollment allows for potential discontinuation of randomization to a specific investigational agent, then the following provides non-binding guidance on how this might be approached:

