10.6.2 Primary Outcome Measures for Phase III

Hospitalization/Death

The cumulative proportion of participants hospitalized or dying during the first 28 days of follow-up will be estimated for each randomized group using Kaplan-Meier methods to take account of losses to follow-up. The difference between randomized groups in the estimated log cumulative proportion will be calculated and the variance for this difference will be obtained using Greenwood's formula. Two-sided 95% confidence intervals (adjusted for multiple interim analyses) and associated p-value for the test of no difference between groups will then be obtained.

Participants who prematurely discontinue the study, who are not able to be contacted by the site to ascertain outcomes after discontinuation, will have follow up censored at the date of last known status.

The above analysis assumes that losses to follow-up are non-informative. As a sensitivity analysis of this assumption, causal inference methods, specifically inverse probability of censoring, may be used.

Safety and Tolerability: Grade 3 or Higher AE

Safety and tolerability will be evaluated by estimating the proportion of participants with new Grade 3 or higher AE(s) by study day 28, and will be compared between groups using binary regression.

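### The primary safety comparison nets drug harm against COVID-19 events prevented, so at the phase III planning rates an effective agent could offset up to about 7.5 added severe AEs per 100

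*Protocol*

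**What the plan says.** - Protocol section 1.1 makes safety co-primary in both phases: "Phases II and III: To evaluate safety of the investigational agent".
- Sections 10.2.1 and 10.2.2 define the primary safety outcome in the same terms: "Safety: New Grade 3 or higher AE through 28 days". No class of event is excluded.
- Sections 10.6.1 and 10.6.2 give one analysis for it, the "proportion of participants with new Grade 3 or higher AE(s) by study day 28, and will be compared between groups using binary regression".
- Section 7.1 counts an AE "REGARDLESS of the attribution (i.e., relationship of event to medical treatment/investigational agent/device or procedure/intervention".
- Section 7.3 adds: "Adverse events resulting from concurrent illnesses, reactions to concurrent illnesses, reactions to concurrent medications, or progression of disease states must also be reported".
- For efficacy, sections 10.4.2 and 10.5.2 plan phase III by "assuming a proportion hospitalized/dying of 15% in the placebo control group and a relative reduction of 50"%, which gives 7.5% on the agent.
- Section 10.6.3 uses the same approach for Grade 2 or higher AEs by day 28 in phase II and Grade 3 or higher AEs by week 24 in phase III.

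**The concern.** Read together, these sections put severe COVID-19 worsening into the primary safety outcome. When the worsening leads to hospitalization or death, it also enters the phase III primary efficacy outcome. The difference between arms in Grade 3 or higher AEs then has two parts of opposite sign: events the agent causes and disease events it prevents. The better the agent works, the more added harm the second part can offset.

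The offset is therefore largest when the agent is effective and likely to be used. A balanced or favourable AE result would then partly be a second readout of efficacy and say little about toxicity. This follows from the primary measure that the protocol itself defines. It does not depend on what the statistical analysis plan may add.

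**Working it through.** **1. The plan's own figures.** The inputs from sections 10.4.2 and 10.5.2 are 15% v 7.5%, 90% power, two-sided 5%, three interim analyses and one final, O'Brien-Fleming-type efficacy boundary, non-binding Gamma(-2) futility, and 5% loss to follow-up.
- Fixed design, unpooled variance: (1.960 + 1.282)² × (0.15×0.85 + 0.075×0.925) / 0.075² = 367.8 per arm.
- Group-sequential inflation by numerical integration is 1.0876: 367.8 × 1.0876 ≈ 400.
- Allowing for loss: 400 / 0.95 ≈ 421 per arm, as stated.
- Expected events: 421 × (0.15 + 0.075) = 94.7, against the stated 95.

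The sample size is not in question. About 400 per arm (421 × 0.95) are taken as evaluable below.

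**2. Size of the offset.** Let s be the share of hospitalizations and deaths that also count as a Grade 3 or higher AE. The protocol makes inpatient hospitalization a criterion for a serious AE (7.1) and leaves grading to an external table (7.2.1), so s is an assumption. If drug-caused and COVID-19 events fall in different participants, the offset is s × (15 − 7.5) per 100:

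| s | Offset per 100 |
|---|---|
| 100% | 7.5 |
| 80% | 6.0 |
| 50% | 3.75 |
| 25% | 1.9 |

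If the two kinds of event occur independently and may overlap, the s = 100% figure is 1 − 0.85/0.925 = 8.1 per 100.

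**3. Chance of seeing 5 points of added harm.** Let b be the background rate of other Grade 3 or higher AEs (assumed 2% to 5%) and t = 0.05 the added harm.
- Placebo: p0 = b + 0.15s. Agent: p1 = b + 0.075s + t.
- SE = √[p0(1−p0)/400 + p1(1−p1)/400].
- Chance of a significant excess at two-sided 5%: 1 − Φ(1.96 − (p1−p0)/SE).

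Example with b = 2% and s = 50%: p0 = 0.095, p1 = 0.1075, difference 0.0125, SE 0.0213. The chance is 1 − Φ(1.37) = 8.5%.

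| s | All-cause, agent effective | All-cause, agent without efficacy (p1 = p0 + t) | COVID-19 events perfectly excluded (b v b + t) |
|---|---|---|---|
| 100% | 0.2% | 40%–43% | 77%–93% |
| 50% | about 8% | 51%–59% | 77%–93% |
| 25% | 31%–40% | 61%–73% | 77%–93% |

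The gap between the first two results columns is due to the offset. The gap between the last two arises because COVID-19 events add variance.

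**4. Larger harm.** With t = 0.075 the all-cause chance is 2.5% (s = 100%), 33%–39% (50%) or 70%–82% (25%). With COVID-19 events excluded it is 97%–99.6%.

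**5. Phase II.** This uses 110 per arm, b = 3% and 10 points of harm, with the agent halving the COVID-19 rate. The all-cause chance at s = 100% is 7% if the placebo COVID-19 rate is 15% and 41% if it is 5%. At 5% and s = 50% it is 59%. With COVID-19 events excluded it is 79%. The 15% is the planning rate for higher-risk participants. Current phase II enrolment is lower-risk, and the protocol gives no rate for that group, so these figures are only illustrative.

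**The case against.** **Left to the analysis plan.** Section 10.6 calls itself an outline, and an AE table without COVID-19 terms is ordinary analysis-plan content. It is true that the absence of such a table from the protocol is not itself an error. But the outcome definition, the AE definition and the comparison are all fixed in the protocol, and together they make the primary measure a net one.

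**No safety test is specified.** Sections 10.6.1 and 10.6.2 give no alpha, null hypothesis or margin for safety, and nothing says that a null result will be read as safe. This stands. The two-sided 5% level used in the working is a reading of the word compared.

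**All-cause counting is defensible.** It avoids judgements about cause and captures net patient benefit. This stands too, and is why the all-cause comparison should remain primary. The 77% to 93% also assumes perfect classification, so it is an upper bound.

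**Other safeguards exist.** The protocol records relatedness and AEs of special interest (7.3), and pauses enrolment for a related death or two related Grade 4 AEs (7.5). The Data and Safety Monitoring Board (DSMB) sees hospitalization/death, deaths and AEs by arm at each phase III interim (10.5.2). These limit the consequence. However, relatedness and the pauses rest on the site investigator's causality call, and section 7.2.2 accepts an event as related only when disease progression does not appear to explain it.

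**Stronger readings.** A reader might infer that the comparison cannot detect relevant harm. At s = 25% it detects 7.5 added points 70% to 82% of the time, so that goes too far. A reader might also note that an effective, non-toxic agent shows significantly fewer AEs 82% to 88% of the time (s = 100%) and call this an inflated error rate. It is not: such an agent truly lowers total severe AEs, and the figure is power for a real net reduction.

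**Conclusion.** The point holds as a limitation of the randomized primary safety comparison. As defined, it estimates harm added minus COVID-19 events prevented. At the phase III planning rates the offset is up to about 7.5 severe AEs per 100, or about 1.9 to 7.5 over assumed shares of 25% to 100%. These figures rest on three assumptions absent from the documents: the share of hospitalizations and deaths graded 3 or higher, a 2% to 5% background rate, and drug-caused events falling in participants other than those with COVID-19 events.

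A flat statement that 7.5 per 100 would be hidden is not supported, because it needs every hospitalization or death to be a Grade 3 or higher AE. Nor do the documents support a claim that safety oversight as a whole is blind. The mechanism applies to phase II as well, but its size there cannot be fixed from the protocol.

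**What to change.** Keep the all-cause Grade 3 or higher comparison as primary. In sections 10.6.1 and 10.6.2, add beside it the same comparison restricted to new Grade 3 or higher AEs that are not COVID-19 disease events or the hospitalization/death endpoint itself. Define the exclusion by a MedDRA term list fixed before unblinding. Report a risk difference with a two-sided 95% confidence interval, give the DSMB both tables, and state that the two results are read together.

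The cost is a wording change, the term list and one more table, from AE data already collected and MedDRA-coded. No participants or visits are added. The downside is that some respiratory events are hard to classify, and disease made worse by the drug would drop out of the restricted comparison. The all-cause result therefore has to stay alongside, and the safety conclusion should not rest on the restricted interval alone.

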10.6.3 Secondary Outcomes

The cumulative proportion of participants dying during the first 28 days of follow-up, and through to 24 weeks, and the cumulative proportion hospitalized/dying through

to 24 weeks will be analyzed in a similar manner to the phase III primary outcome. Analysis of the proportion of participants with new Grade 2 or higher AE(s) by day 28 in phase II, and new Grade 3 or higher AE(s) by week 24 in phase III, and the proportion with progression of symptoms, will be undertaken using the same approach as for the primary safety analysis.

The duration of time to self-reported return to usual health will be analyzed using similar methods as for the analysis of symptom durations.

The AUC virologic outcome, COVID-19 severity ranking, will be compared between arms using a Wilcoxon test, with descriptive summaries of the distribution of these outcome measures among participants.

Levels of SARS-CoV-2 RNA on days 3, 7, 14, and 28 will be compared between arms using non-parametric Wilcoxon rank-sum tests and descriptive statistics, separately at each scheduled measurement time (considering RNA results below assay limit as the lowest rank).

Descriptive summaries of clinical outcomes among those hospitalized will be provided by arm, recognizing that this would not be a randomized comparison, if restricted to participants who were hospitalized.

10.7 Unblinding

Unblinding requests will follow PPD procedures.

In general, participants who become hospitalized at any time during the study period of 24 weeks can have their individual study treatment unblinded if essential for their future treatment management or if necessary for enrollment into a COVID-19 treatment clinical trial. This determination should be made by the Investigator of Record at the trial site and documented on the eCRF.

If treatment assignment is unblinded, this information should only be shared with the physicians responsible for the management of the participant on a need-to-know basis. Treatment assignment should not be shared with others. This includes not sharing treatment assignment with the study team.

11.0 PHARMACOLOGY PLAN

The phase II pharmacology objective is to determine the pharmacokinetics of the investigational agent. For phases II and III, the pharmacology objective is to explore relationships between dose and concentration of investigational agent with virology, symptoms, and oxygenation. Samples for quantification of concentrations of the investigational agent will be obtained using a collection schedule appropriate for that agent and phase of evaluation, taking into consideration known pharmacokinetic

characteristics (e.g., elimination half-life). Pharmacokinetic data analysis will use conventional and accepted approaches such as non-compartmental analysis, compartmental analysis, and population approaches. Usual parameters of interest are area under the concentration-time curve (AUC), total or apparent body clearance (CL), elimination half-life ($T_{1/2}$), and maximum and minimum concentrations (C_{max} , C_{min}). Exploration of relationships between dose and concentration of investigational agent with virology, symptoms, and oxygenation will be approached using conventional and accepted methods for pharmacokinetic/pharmacodynamic (PK/PD) data analyses. Such methods might include the E_{max} or sigmoid E_{max} model or structurally linked PK/PD models to explore exposure-response relationships. Exposure-response relationships will be performed in conjunction with the protocol statisticians.

See relevant appendix/appendices for details of the agent-specific pharmacology plan.

12.0 DATA COLLECTION AND MONITORING

12.1 Data Quality Assurance

This study will be conducted according to the ICH E6(R2) risk and quality processes described in the applicable procedural documents. The quality management approach to be implemented in this study will be documented and will comply with the current ICH guidance on quality and risk management. The sponsor assumes accountability for actions delegated to other individuals (e.g., Contract Research Organizations).

12.2 Records to Be Kept

Electronic case report form (eCRF) screens will be made available to sites for data entry. Participants must not be identified by name on any data submitted to the DMC. Participants will be identified by the subject number provided by the Clinical Data Management System (CDMS) upon enrollment.

12.3 Role of Data Management

As part of the responsibilities assumed by participating in the study, the investigator agrees to maintain adequate case histories for the participants treated as part of the research under this protocol. The investigator agrees to maintain accurate eCRFs and source documentation as part of the case histories.

All eCRF information is to be filled in. If an item is not available or is not applicable, this fact should be indicated. Blank spaces should not be present unless otherwise directed.

Investigative site personnel will enter participant data into CDMS. The analysis data sets will be a combination of these data and data from other sources (e.g., laboratory data).

Clinical data management will be performed in accordance with applicable DAIDS and PPD standards and data cleaning procedures to ensure the integrity of the data, for example, removing errors and inconsistencies in the data. Adverse event terms will be coded using MedDRA, an internal validated medical dictionary, and concomitant medications will be coded using WHODRUG.

12.4 Clinical Site Monitoring and Record Availability

12.4.1 Site monitors under contract to the NIAID will visit participating clinical research sites to review the individual participant records, including consent forms, eCRFs, supporting data, laboratory specimen records, and medical records (physicians' progress notes, nurses' notes, individuals' hospital charts), to ensure protection of study participants, compliance with the protocol, and accuracy and completeness of records. The monitors also will inspect sites' regulatory files to ensure that regulatory requirements are being followed and sites' pharmacies to review product storage and management.

Monitoring visits may be conducted on-site or remotely. Remote visits may include remote source document verification using methods specified for this purpose by NIAID. Remote monitoring visits may be performed in place of, or in addition to onsite visits to ensure the safety of study participants and data integrity [17]. The site will make available study documents for site monitors to review utilizing a secure platform that is HIPAA and 21 CFR Part 11 compliant. Potential platform options include: Veeva SiteVault, site-controlled SharePoint or cloud-based portal, direct access to Electronic Medical Record (EMR), and Medidata Rave Imaging Solution. Other secure platforms that are 21 CFR Part 11 compliant may be utilized, as allowed by the DAIDS Office of Clinical Site Oversight (OCSO).

12.4.2 The site investigator will make study documents (e.g., consent forms, drug distribution forms, eCRFs) and pertinent hospital or clinic records readily available for inspection by the local IRB/IEC, the site monitors, the FDA, the NIAID, the ACTG, the OHRP, the industry supporter(s) or designee (as appropriate), other local, US, and international regulatory authorities/entities for confirmation of the study data.

